5.1.1.1.4 Missing Data

There will be no imputation of missing data for all analyses.

Table 5-3 Missing Data Handling by Endpoint Type

| Endpoint type | Timing | Missing Data Handling |
|------------------|------------------|---|
| Responder | Treatment Period | 
 • All patients included • Patients with no postbaseline values will be excluded |
| CFB ANCOVA | Treatment Period | 
 • If missing covariates (including baseline if applicable) 
 ○ Subject excluded • If missing average change from baseline UNVA letters: 
 ○ Subject excluded |
| CFB Posebaseline | Treatment Period | 
 • If missing value at the specified postbaseline analysis visit: 
 ○ Available cases 
 ▪ Subject excluded |

ANCOVA = analysis of covariance; CFB = change from baseline

5.1.1.1.5 Site Pooling

Data from all sites will be pooled for analysis.

5.1.1.1.6 Other Common Conventions

Ocular adverse events and other ocular evaluations will be summarized using eye as the experimental unit by treatment group. Nonocular adverse events and other nonocular assessments will be summarized using patient as the experimental unit by treatment group.

5.1.1.2 Demographics

5.1.1.2.1 Analysis Populations

The distribution of patients within the analysis populations will be summarized as follows:

Table 5-4 Analysis Population Summaries

| Population | Description | Timing | Methodology |
|-----------------------------|---|------------------|--------------------|
| Screened Population | Distribution overall and within countries/regions/sites in total | Screening Period | Categorical counts |
| mITT and Safety populations | Distribution overall and within countries/regions/sites in total and by treatment group | Treatment Period | Categorical counts |

5.1.1.2.2 Participant Disposition

Subject disposition encompasses the distribution of patients who enter, complete, and discontinue each specified analysis period, along with electric case report form (eCRF)-reported discontinuation reasons from each respective analysis period. Subject disposition will be summarized as follows:

Table 5-5 Subject Disposition Summaries

| Parameter | Description | Timing | Methodology |
|-----------------------|---|------------------|-------------------------|
| Screening disposition | Distribution in the Screened Population in total | Screening Period | Categorical descriptive |
| Study disposition | Distribution in the mITT Population in total and by treatment group | Treatment Period | Categorical descriptive |

mITT = modified intent-to-treat

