4.1 Number of Patients

Approximately 150 patients (30 per group) will be enrolled at approximately 15 sites in the US. Approximately 26 patients per group are expected to complete the study based on an anticipated dropout rate of less than 12.5%. Approximately two-thirds of the enrolled patients will be \leq 50 years old.

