5.4 Treatment Allocation Ratio and Stratification

Patients will be randomized in a 1:1:1:1:1 ratio into 1 of 5 treatment groups:

- Group 1: Vehicle control, OU
- Group 2: Fixed combination AGN 199201 (██████████) and AGN 190584 (██████████), OU
- Group 3: Fixed combination AGN 199201 (██████████) and AGN 190584 (██████████), OU
- Group 4: Fixed combination AGN 199201 (██████████) and AGN 190584 (██████████), OU
- Group 5: Fixed combination AGN 199201 (██████████) and AGN 190584 (██████████),
monocular dosing to the nondominant eye and vehicle to the dominant eye

Randomization will be stratified by age (2 groups: ≤ 50 and > 50) and iris color (2 groups: brown and not brown) at the baseline visit. There will be a total of 4 strata; brown eyes and age ≤ 50 years, brown eyes and age > 50 years, not brown eyes and age ≤ 50 years, and not brown eyes and age > 50 years. For the determination of stratification group assignment for each patient, sites will be required to enter iris color (ie, brown, blue, green, gray, or hazel) and age into the Interactive Response System (IxRS), and the IxRS will assign the stratum.

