7.1 Analysis Populations

The modified intent-to-treat (mITT) population will be defined as all randomized patients with a baseline and at least 1 postbaseline assessment of mesopic, high contrast UNVA and will be analyzed as randomized. The efficacy variables will be analyzed using the mITT population.

The safety population will be defined as all patients who received at least 1 dose of study treatment. Safety analyses will be performed on an as-treated basis. All safety measures will be analyzed using the safety population.

Approval Date: 18-Aug-2016

In general, continuous data will be summarized with descriptive statistics (number of patients, mean, standard deviation, median, minimum, and maximum) and will be analyzed using analysis of covariance (ANCOVA) or 2-sample t-tests. Categorical variables will be summarized by sample size (N), frequency count and percent, and will be analyzed using Pearson's chi-square, Fisher's exact, or the Cochran-Mantel-Haenszel (CMH) test.

There will be no imputation of missing data for all analyses.

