8.3 Procedures for Final Study Entry

The results from screening ocular examinations must be evaluated and determined to be acceptable to the investigator prior to the patient’s entry into the study. Furthermore, all female patients of childbearing potential MUST have a negative urine pregnancy test at screening and baseline (day 1) prior to randomization and initiation of study treatment. Each patient’s ocular examination findings at screening and baseline (day 1) will be evaluated with respect to the entry criteria specified in Sections 4.3 and 4.4 for final determination of eligibility before the patient is randomized.

Patients will be considered to have enrolled in the study when they are randomized.

See Section 5.5 for the method for assignment to treatment groups/randomization.

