5.1.1.1 Common Conventions

5.1.1.1.1 Analysis Populations

The analysis populations will consist of patients as defined below: See [Table 5-1](#).

Table 5-1 Analysis Populations

| Population | Definition | Study Treatment |
|---------------------------------|--|-----------------------|
| Screened | All screened patients who sign informed consent | — |
| Modified Intent-to-Treat (mITT) | All randomized patients with a baseline and at least 1 post baseline assessment of mesopic, high contrast, UNVA and will be analyzed as randomized | Randomized assignment |
| Safety | All patients who received ≥ 1 administration of study treatment and will be analyzed as treated | Actual received |

The efficacy variables will be analyzed using the mITT population. All safety measures will be analyzed using the safety population.

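### Disposition and important deviations are tabulated on mITT, so randomized patients lacking a baseline or postbaseline UNVA drop out of both tables; discontinuation would be understated if anyone leaves before a postbaseline UNVA

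*SAP*

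**What the plan says.** SAP 5.1.1.2.2 says disposition covers "the distribution of patients who enter, complete, and discontinue each specified analysis period", together with the discontinuation reasons recorded on the eCRF. Table 5-5 then fixes the population for study disposition: "Distribution in the mITT Population in total and by treatment group". Table 5-6 (SAP 5.1.1.2.3) gives the same population, in the same words, for important protocol deviations.

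SAP Table 5-1 defines mITT as "All randomized patients with a baseline and at least 1 post baseline assessment of mesopic, high contrast, UNVA". Protocol 7.1 agrees: "all randomized patients with a baseline and at least 1 postbaseline assessment of mesopic, high contrast UNVA". SAP Table 5-13 places the baseline for this measure at Day 1, Hour 0.

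Protocol 8.3 sets the point of enrolment: "Patients will be considered to have enrolled in the study when they are randomized". Protocol 8.8 requires each early discontinuation and its reason to be documented on the eCRF, and Protocol 8.9 says withdrawn patients are not replaced.

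The SAP defines three populations only: Screened, mITT and Safety. Table 5-4 counts patients in each, with mITT and Safety split by treatment group. Table 5-25 summarises adverse events leading to discontinuation on the Safety population.

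**The concern.** A disposition table should account for every patient who entered. Here, entry to the table depends on having completed an efficacy assessment after baseline. A patient who is randomized and leaves before that assessment has a discontinuation reason on the eCRF, but is missing from the entered count, the discontinued count and the reasons. A patient randomized without a Day 1, Hour 0 UNVA is missing as well.

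The deviations table has a related weakness. A missed baseline assessment, or randomization without dosing or assessment, may itself be a deviation, yet the same event removes the patient from Table 5-6. Whether it would be classed as important cannot be seen, because the classification is kept in a separate document.

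Tolerability is part of the first two study objectives, and Protocol 1.3 draws a tolerability argument from discontinuation rates (4.6% with a combination against 20% to 25% with pilocarpine monotherapy). A rate that leaves out the earliest leavers is not on the same footing as one over everyone who started. If the omissions differ by arm, the between-arm picture is distorted too.

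**Working it through.** **Inputs**
- Planned size: "Approximately 150 patients (30 per group) will be enrolled at approximately 15 sites in the US" (Protocol 4.1), with equal allocation to five groups (Protocol 5.4).
- Dropout allowance: below 12.5%, 26 completers per group (Protocol 4.1), given as 4 dropped patients per group in the Protocol Summary.
- Number k of dropouts per group who leave before any postbaseline UNVA: not in the documents. It is an assumption, shown from 0 to 4.

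**The plan's own figure.** Completers per group = 30 × (1 − 0.125) = 26.25, stated as 26. In reverse, 26 / (1 − 0.125) = 29.7, rounded up to 30. The planning figures reproduce. (Four of 30 is 13.3%, slightly above the stated 12.5%; this is rounding and does not matter here.)

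**Effect on the discontinuation rate.** Let n be randomized and d discontinued. Over all randomized patients the rate is d/n. On mITT it is (d − k)/(n − k). For k > 0, (d − k)/(n − k) < d/n is equivalent to n(d − k) < d(n − k), that is, d < n. So whenever at least one patient in the group stays, early leavers can only lower the reported rate.

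With n = 30 and d = 4:

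| k (assumed) | mITT rate | All-randomized rate |
|---|---|---|
| 0 | 4/30 = 13.3% | 13.3% |
| 1 | 3/29 = 10.3% | 13.3% |
| 2 | 2/28 = 7.1% | 13.3% |
| 3 | 1/27 = 3.7% | 13.3% |
| 4 | 0/26 = 0% | 13.3% |

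One omitted patient moves a group's rate by about 3 percentage points (13.3 − 10.3). The same k in every group gives the same rates overall; for example, 20/150 = 13.3% becomes 15/145 = 10.3% with k = 1 per group.

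**Missing baseline.** If a patient is excluded only because the baseline UNVA is missing and goes on to complete, the rate moves slightly up: 4/29 = 13.8% against 13.3%.

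**Deviations.** The patients omitted from Table 5-6 are the same, but the documents do not say how many would have an important deviation, so no direction can be derived.

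**Can another visible table fill the gap?**
- Screening disposition (Table 5-5) covers the Screened population in total, not by arm, and only the Screening Period.
- Table 5-4 gives mITT and Safety counts by arm, but no all-randomized count and no reasons for exclusion. Its two counts also follow different rules: mITT as randomized, Safety as treated.
- Table 5-25 captures an early leaver only if the patient was dosed and left because of an adverse event. That patient would then count as an adverse-event discontinuation and be missing from disposition, so the two tables may not agree.

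**The case against.** The strongest reply is that k may be zero. One postbaseline UNVA at any time is enough to enter mITT. Randomization and the first in-clinic dose both take place at visit 1 (Protocol 5.5 and 5.6), and SAP 5.2.2 shows that UNVA is measured at several postdose timepoints. If any of these fall on Day 1, only a patient who leaves within hours of the first drop is lost, and one who stops a few days later stays in the table. The visit schedule is redacted, so this can be neither confirmed nor ruled out. It stands as a limit on the size of the problem. So does the prior study, where 2 of 65 patients discontinued in total (Protocol 1.3): four dropouts per group is a planning allowance, not a forecast.

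A reader might also infer that the plan hides tolerability dropouts and any imbalance between arms in exclusion from mITT. The documents do not support that. Adverse events leading to discontinuation are tabulated by arm on the Safety population, and those patients are listed. Table 5-4 lets a reader subtract mITT from Safety by arm, and with in-clinic dosing at visit 1 the Safety count should be close to the randomized count. What remains hidden is early withdrawal for other reasons, patients never dosed, and the reasons for exclusion.

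Finally, table and listing specifications sit in a separate document, so a footnote or listing may already account for these patients. That is possible, but the SAP text does not call for it.

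**Conclusion.** The point holds as a conditional reporting weakness. Tables 5-5 and 5-6 name a population that can omit randomized patients, and no visible table restores them by arm.

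If any patient discontinues before a postbaseline UNVA, the discontinuation rate is understated, by about 3 percentage points in a group for one such patient under the 4-in-30 allowance. That size rests on an assumed k and on the planning dropout figure; with k = 0 and no missing baselines, the two rates coincide.

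It would be tempting to say that the reported rate is biased downward as a matter of fact. The documents do not support this: k is not given, and exclusion for a missing baseline can move the rate the other way. Nor can any direction be claimed for important deviations. The primary efficacy analysis and the power calculation do not use these tables and are unaffected.

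**What to change.** In SAP Table 5-5 (study disposition row) and Table 5-6, replace the mITT population with all randomized patients, in total and by randomized group. Add, in Table 5-4 or in the disposition table, a by-arm count of randomized patients excluded from mITT and from Safety, with the reasons. Make the change before database lock.

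The cost is two changed population flags, one added summary and the matching edits to the table specifications. The reported discontinuation rate may look slightly less favourable. If nobody is excluded, no rate changes and the report can show that.

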5.1.1.2.3 Protocol Deviations

Protocol deviations will be defined in a separate document, including importance classification. Protocol deviations will be summarized as follows:

Table 5-6 Protocol Deviation Summary

| Parameter | Description | Timing | Methodology |
|-------------------------------|---|------------------|-------------------------|
| Important protocol deviations | Distribution in the mITT Population in total and by treatment group | Treatment Period | Categorical descriptive |

5.1.1.2.4 Demographics

Demographics will be summarized for the Screened Population, and in total and by treatment group for the mITT and Safety populations, as follows:

Table 5-7 Demographic Summaries

| Parameter | Description | Timing | Methodology |
|--------------------------|--|------------------|--------------------------|
| Age | Age (years) relative to informed consent date | Informed consent | Continuous descriptives |
| Age group | 
 • ≤ 50 years • > 50 years | Informed consent | Categorical descriptives |
| Sex, race, and ethnicity | 
 • eCRF categories • Race group 
 ○ White ○ Non-white • Ethnicity 
 ○ Hispanic ○ Non-hispanic | Screening Period | Categorical descriptives |

5.1.1.2.5 Baseline Characteristics

Baseline characteristics will be summarized in total and by treatment group for the mITT and Safety populations as follows:

Table 5-8 Baseline Characteristics Summaries

| Parameter | Description | Timing | Methodology |
|--------------------------|--|----------------------|-------------|
| Baseline characteristics | 
 • Iris color | Latest assessment in | Categorical |

| Parameter | Description | Timing | Methodology |
|----------------------|---|---|--------------------------|
| | | Screening Period or Pretreatment Period | descriptives |
| Randomization strata | 
 UNVA severity at baseline ($\leq 20/80$ and $> 20/80$) | Randomization date | Categorical descriptives |
| Baseline efficacy | 
 Mesopic pupil diameter with Grand Seiko sites vs without Grand Seiko sites UNVA severity at baseline with Grand Seiko sites vs without Grand Seiko sites | Randomization date | Continuous descriptives |

5.1.1.2.6 Medical History

Medical history, encompassing abnormalities and surgeries reported as occurring before the Screening Visit, will be coded using the Medical Dictionary for Regulatory Activities (MedDRA), version 19.0 or newer. Unique patients who report medical history events will be summarized by MedDRA system organ class (SOC) and preferred term (PT) by treatment group for the Safety Population as follows:

Table 5-9 Medical History Summary

| Parameter | Description | Timing | Methodology |
|------------------------------|--|------------------|-------------------------|
| Medical and surgical history | Abnormalities and surgeries occurring before the Screening Visit | Screening Period | Categorical descriptive |

SOCs will be sorted alphabetically; PTs will be sorted in descending frequency in the highest dose group.

5.1.1.2.7 Ophthalmic History and Ophthalmic Surgical History

Ophthalmic history, encompassing abnormalities and ophthalmic surgeries reported as occurring before the Screening Visit, will be coded using MedDRA, version 19.0 or newer. Unique patients who report ophthalmic history events will be summarized by MedDRA SOC and PT by treatment group for the Safety Population as follows:

Table 5-10 Ophthalmic History and Ophthalmic Surgery History Summary

| Parameter | Description | Timing | Methodology |
|---|--|------------------|-------------------------|
| Ophthalmic history and ophthalmic surgery history | Abnormalities and surgeries occurring before the Screening Visit | Screening Period | Categorical descriptive |

SOCs will be sorted alphabetically; PTs will be sorted in descending frequency in the highest dose group.

5.1.1.2.8 Prior and Concomitant Medications

Medications will be listed for the Safety Population as follows:

Medications will be coded using the World Health Organization (WHO) Drug Dictionary, version 14.0 or newer. Unique patients who reported medications will be summarized by

Anatomical Therapeutic Chemical (ATC) 4 class and PT by treatment group for the Safety Population as follows:

Table 5-11 Medication Summaries

[figure not shown]
| Parameter | Description | Timing | Methodology |
|-------------------------|---|---------------------------------------|--------------------------|
| Prior medications | Medications taken ≥ 1 time before the study treatment start date, regardless of medication end date | Screening Period, Pretreatment Period | Categorical descriptives |
| Concomitant medications | Medications taken ≥ 1 time on or after the study treatment start date, regardless of medication start date 
Medications starting 1 day after treatment end date will be listed but excluded from analysis | Treatment Period, Follow-up Period | Categorical descriptives |

ATC4 classes will be sorted alphabetically; PTs will be sorted in descending frequency in the highest dose group.

5.1.1.3 Efficacy Analyses

Efficacy analyses will be based on the mITT Population.

The following efficacy assessments are defined:

Baseline assessments for applicable efficacy endpoints defined as follows:

Table 5-13 Efficacy Endpoint Baseline Definitions

| Endpoint | Description | Timing |
|---|---|--------------|
| 
 Mesopic, high contrast UNVA | Non-missing measurements at Day 1 Hour 0 
 Patients with no Day 1 Hour 0 measurement will be excluded from CFB analyses¹ | Day 1 Hour 0 |
| [Redacted Content] | | |

5.1.1.3.1 Study Success Criteria

[figure not shown]
[figure not shown]
There will be no adjustment of type 1 error rate for the multiple tests. There will be no imputation of missing data for all analyses.

[figure not shown]
5.1.1.3.2 Mesopic, High Contrast UNVA

[figure not shown]
Mesopic, high contrast UNVA endpoints will be summarized by treatment group for mITT Population.

[figure not shown]
Table 5-14 Mesopic, High Contrast UNVA

| Endpoint | Description | Timing | Methodology |
|--|--|-------------------------|------------------------------------|
| Average change from baseline in UNVA letters (Primary efficacy variable) | Average change from baseline in UNVA lines in the nondominant eye at day 28. | Treatment Period Day 28 | CFB ANCOVA ¹ CFB figure |
| [Redacted] | [Redacted] | [Redacted] | [Redacted] |
| [Redacted] | [Redacted] | [Redacted] | [Redacted] |

5.1.1.4.2 Adverse Events

The following adverse event (AE) terms are defined:

Table 5-24 AE Terms

| Term | Description |
|--------------------|---|
| Treatment-emergent | An event that initially occurs or increases in intensity on or after the treatment start date, where: 
 Treatment start date \leq event start date \leq treatment end date + 30 |
| On-therapy | An event where: 
 Treatment start date \leq event start date \leq treatment end date + 30 |

AEs, encompassing abnormalities and surgeries reported as occurring after the Screening Visit, will be coded using MedDRA version 19.0 or newer. Unique patients reporting AEs in the following AE categories will be summarized by treatment group and overall for the Safety Population as follows:

[figure not shown]
Table 5-25 AE Summaries

[figure not shown]
| Parameter | Description | Timing | Methodology |
|---------------------|--|------------------------------------|--------------------------|
| Overall summary | Overall summary only for the following categories: 
 Treatment-emergent AEs (TEAEs) Treatment-related TEAEs Study-procedure-related TEAEs On-therapy serious adverse events (SAEs) On-therapy fatal SAEs AEs leading to discontinuation | Treatment Period, Follow-up Period | Categorical descriptives |
| TEAEs | Overall summary and by SOC and PT | Treatment Period, Follow-up Period | Categorical descriptives |
| Ocular TEAEs | Summary by SOC and PT for ocular TEAEs dominant eye nondominant eye | Treatment Period, Follow-up Period | Categorical descriptives |
| Non-ocular TEAEs | Summary by SOC and PT for non-ocular TEAEs | Treatment Period, Follow-up Period | Categorical descriptives |
| Common TEAEs | Summary by PT 
 Includes TEAEs occurring in \geq 5.0% of patients in any treatment group | Treatment Period, Follow-up Period | Categorical descriptives |
| Common Ocular TEAEs | Summary by PT for common ocular TEAEs dominant eye | Treatment Period, Follow-up Period | Categorical descriptives |

[figure not shown]
| Parameter | Description | Timing | Methodology |
|--|--|------------------------------------|--------------------------|
| | nondominant eye | | |
| Common Non-ocular TEAEs | Summary by PT for common non-ocular TEAEs | Treatment Period, Follow-up Period | Categorical descriptives |
| TEAEs by intensity | Overall summary and by SOC, PT, and intensity 
 Patients categorized overall and within each SOC and PT for the most intense occurrence | Treatment Period, Follow-up Period | Categorical descriptives |
| Ocular TEAEs by intensity | Overall summary and by SOC, PT, and intensity for ocular TEAEs 
 Patients categorized overall and within each SOC and PT for the most intense occurrence dominant eye nondominant eye | Treatment Period, Follow-up Period | Categorical descriptives |
| Non-ocular TEAEs by intensity | Overall summary and by SOC, PT, and intensity for non-ocular TEAEs 
 Patients categorized overall and within each SOC and PT for the most intense occurrence | Treatment Period, Follow-up Period | Categorical descriptives |
| Treatment-related TEAEs | Overall summary and by PT | Treatment Period, Follow-up Period | Categorical descriptives |
| Ocular Treatment-related TEAEs | Overall summary and by PT for ocular TEAEs dominant eye nondominant eye | Treatment Period, Follow-up Period | Categorical descriptives |
| Non-ocular Treatment-related TEAEs | Overall summary and by PT for non-ocular TEAEs | Treatment Period, Follow-up Period | Categorical descriptives |
| Study-procedure-related TEAEs | Overall summary and by PT | Treatment Period, Follow-up Period | Categorical descriptives |
| Ocular Study-procedure-related TEAEs | Overall summary and by PT for ocular TEAEs dominant eye nondominant eye | Treatment Period, Follow-up Period | Categorical descriptives |
| Non-ocular Study-procedure-related TEAEs | Overall summary and by PT for non-ocular TEAEs | Treatment Period, Follow-up Period | Categorical descriptives |
| On-therapy SAEs ¹ | Overall summary and by PT | Treatment Period, Follow-up Period | Categorical descriptives |
| On-therapy ocular SAEs | Overall summary and by PT for ocular SAEs dominant eye nondominant eye | Treatment Period, Follow-up Period | Categorical descriptives |
| On-therapy non-ocular SAEs | Overall summary and by PT for non-ocular SAEs | Treatment Period, Follow-up Period | Categorical descriptives |
| On-therapy fatal SAEs ¹ | Overall summary and by PT | Treatment Period, Follow-up Period | Categorical descriptives |
| On-therapy fatal ocular SAEs | Overall summary and by PT for ocular fatal SAEs dominant eye nondominant eye | Treatment Period, Follow-up Period | Categorical descriptives |
| On-therapy fatal non-ocular SAEs | Overall summary and by PT for non-ocular fatal SAEs | Treatment Period, Follow-up Period | Categorical descriptives |

[figure not shown]
| Parameter | Description | Timing | Methodology |
|---|--|---------------------------------------|--|
| AEs leading to study discontinuation ¹ | Overall summary and by PT | Treatment Period, Follow-up Period | Categorical descriptives |
| Ocular AEs leading to study discontinuation | Overall summary and by PT for ocular AEs leading to discontinuation dominant eye nondominant eye | Treatment Period, Follow-up Period | Categorical descriptives |
| Non-ocular AEs leading to study discontinuation | Overall summary and by PT for non-ocular AEs leading to discontinuation | Treatment Period, Follow-up Period | Categorical descriptives |

[figure not shown]
¹ Patients who report ≥ 1 AE in the AE category and all AEs for those patients will be listed. SOCs will be sorted alphabetically; PTs will be sorted in descending frequency in the highest dose group.

[figure not shown]

